2.3.2 Analysis of impact of Disclosure (Genetic Disclosure and Amyloid Disclosure)

Background

The intention of this section is to summarize the main safety evaluation of Genetic and Amyloid Disclosure follow-up in CNP520A2202J. No inferential statistical analyses will be reported. Disclosure assessment scales, baseline characteristics and all other safety assessment related to disclosure will be reported descriptively as appropriate.

Safety assessments will include disclosure scales, eC-SSRS, adverse events (AEs), and serious adverse events (SAEs) if related to genetic disclosure. The statement that a participant had no adverse event or findings also constitutes a safety assessment.

Summary statistics for categorical data will typically include frequencies and percentages per selected group.

Assessment period for impact of Disclosure

The Screening Epoch of study CNP520A2202J includes several visits, separable into two parts: screening part I and screening part II. Screening part I will have APOE genotype assessed. After genetic counseling and disclosure, participant may take a few days to reflect on this information, before continuing to screening part II. A follow up will take place two to seven days post genetic disclosure. Screening part II starts after the reflection period, and contains MRI scan, amyloid PET scan or a lumbar puncture to verify eligibility of HTs based on brain amyloid status (HTs can opt out of amyloid disclosure). Another reflection period may take place after amyloid disclosure. A follow up will take place two to seven days post disclosure

Throughout the disclosure follow-up periods of CNP520A2202J, an independent Disclosure Monitoring Advisory Group (DMAG) is responsible for monitoring the safety of the participants in relation to the Genetic and Amyloid disclosure. DMAG review the disclosure data twice a year to ensure that any outstanding safety concerns would be properly addressed. A separate analysis plan specifies the analyses to be performed for the DMAG reviews. This genetic and amyloid disclosure CSR will be largely overlapping the DMAG.

[figure not shown]
The impact of genetic disclosure is assessed 2-7 days after the genetic disclosure (GD). The

[REDACTED]

[REDACTED]

[REDACTED]

[REDACTED]

Analysis strategy

Data for impact of GD and AmD will typically be reported based on the corresponding Follow-up set by APOE4 genotype and/or Amyloid status.

Note: In database, APOE genotype data is collected from two sources; CRF and vendor (Covance) load. CRF data is for initial genotyping and vendor load is for genotype confirmation. For reporting of genetic disclosure analysis, CRF data will be used to derive the genotype. However, if the CRF data is missing, the corresponding vendor load data will be used.

Amyloid status will be Elevated/Not-Elevated as derived by vendor result (including a visual examination of the scan).

[figure not shown]
The reference visit for change from “baseline” for impact of GD questionnaires will be the Screening 1 Visit 101 (pre-GD assessment) for reports on the impact of GD. The corresponding reference value is defined as the last value collected before GD, i.e. the value collected at the Screening 1 visit. The Screening 3 Visit 103 (Day 2-7 after GD) will be the reference visit for

reports on the impact of AmD. Nevertheless, the reference value can also stem from an earlier visit. The reference value is defined as the last value collected before AmD, i.e. the value from the last assessment from the last visit before or at the reference visit.

Note: For roll over participants whose assessments corresponding to Screening 1 and Screening 3 visits in GS2 are performed in GS1. However, in GS2 at least one assessment is required before amyloid disclosure and it may be recorded under Screening 1 or Screening 3, hence the change from baseline will be derived as described earlier using for reference value the last value collected before AmD, i.e. the value from the last assessment from the last visit before or at the reference visit.

The number and percentage of participants in each analysis set described above will be presented including all participants that started screening. Reason for screen failure will be listed for all screened participants.

Demographic information will be summarized such as age, gender, prior knowledge of genotype, years of education, family history of AD based on the disclosure Follow-up set.

Adverse events (AEs)

AEs and SAEs identified by the investigator as being related to disclosure will be summarized.

In addition, all AEs related to disclosure will be listed as well as concomitant medications of these participants. Results of the impact of disclosure questionnaires will be listed by visit for these participants.

AEs that may be related to genetic or amyloid disclosure may consist of, but not limited to the following:

- Depression per investigator judgment (and GDS total score >10)
- Anxiety per investigator judgment (and score on the six Item Subset of the STAI-AD >19 at any of the Post-Disclosure Follow-up phone calls)
- Increase in levels of distress per investigator judgment (as reported as AE since no specific scale in GS2).
- Suicidality

Participants meeting any of thresholds in [Table 2-2](#) will be referred for additional follow-up with a psychiatrist, corresponding AE will be recorded and any concomitant medication. In case the assessments were administered over the phone, an unscheduled visit to the site is warranted to collect appropriate safety measures.

eC-SSRS

In addition to the above listed specific questionnaires to assess the impact of genetic and amyloid disclosure, suicidality (ideation and behavior) will be collected as part of the “Screening epoch” of CNP520A2202J. The Columbia-Suicide Severity Rating Scale (C-SSRS) is a questionnaire that prospectively assesses Suicidal Ideation and Suicidal Behavior. If, at any time the score is “yes” on item four or item five of the Suicidal Ideation section of the eC-SSRS (and if at Screening, the ideation occurred in the past 6-months) or “yes” on any item of the Suicidal Behavior section, the participants must be referred to a psychiatrist for further assessment and/or treatment if the investigator is not a certified psychiatrist. More details about eC-SSRS can be found in study protocol.

The eC-SSRS data will also be reported using the same strategy as in DMAG.

Two analysis periods will be defined and used as follows:

1. Lifetime history:

Lifetime assessment occurs only once, Screening 1 visit (Visit 101).

2. Post disclosure pre-treatment period:

Assessments after the Screening 1 visit (Visit 103, Visit 107) up to and including the baseline visit ((Visit 201) and unscheduled visit falling into 12-week Screening period).

First assessment of eC-SSRS is SCREENING 1 (V101) in CCNP520A2202J study.

In CNP520A2202J, eC-SSRS is collected in all screened participants and will, hence, be reported based on the Screened set. The number and percentage of participants in each category will be tabulated by visit for categorical data and summary statistics will be presented for continuous data.

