Altogether, the screening period (part I and part II, including reflection periods when required) is expected to last about 12 weeks. The screening period can be extended on a case-by-case basis to accommodate scheduling. In such case see [Section 6.1](#) for guidance on assessments to be repeated to ensure continued eligibility during extended screening.

The assessments to be performed are listed in the assessment schedule ([Table 6-1](#)) and include assessments to be performed by the investigator/study site personnel, participant and study partner (see definition of study partner and role of key study site personnel in [Appendix 2](#)).

Treatment

Participants who are randomized to the study will receive the investigational treatment or placebo for variable treatment duration: at least 60 months, and up to an expected maximum of 96 months (see [Section 3.3](#)).

During the treatment period participants will return to the study site every three months for drug dispensing. The measurements to assess efficacy endpoints are performed at 3 months and 6 months during the first year and then every six months, and include various cognitive and neuropsychological scales with input from the study partner. Although the study partner is expected to come to the site with the participant to all relevant visits, if that proves impossible, his/her input can be obtain by telephone interview.

Safety related assessments will include regular standard assessments (e.g. eC-SSRS, vital signs physical evaluation, laboratory tests, electrocardiograms (ECGs)), as well as specific assessments related to potential CNS or other safety assessment requirements (skin photographs and pruritus evaluation, neurological evaluations, brain MRI scans for monitoring of cerebrovascular pathology and detection of ARIA) are conducted according to the schedule shown in [Table 6-1](#). Brain MRI scans will be read centrally at the Imaging Central Review Vendor, with safety reports provided to the Investigators and Novartis Medical Monitor. Guidance to the Investigators in case of new findings is provided in [Section 13.2](#).

████████████████████ and AD biomarkers; and tau PET scans (expected at the subset of sites that can participate) are performed according to the schedule shown in [Table 6-1](#).

Voluntary assessments, include amyloid PET scan and/or lumbar puncture (for biomarkers ██████████) ██████████.

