6.1.6.1 Screening extensions beyond 12 weeks

The total duration of 12 weeks for screening assessments may be extended only if the following conditions are met:

- The participant has not failed any eligibility criteria (if so, see [Section 6.1.6](#) for potential re-screening in case of temporary conditions).
- Any screening (including Baseline) assessment supporting eligibility criteria must be performed within 12 weeks before the date of randomization. Assessments that are collected again during screening/baseline per [Table 6-1](#), can be used to verify eligibility in the 12 week timeframe, with an exception for MRI that can support eligibility if collected within 16 weeks before randomization. Screening results from amyloid PET scan or lumbar puncture to verify brain amyloid levels are valid without any limitation and do not need to be repeated before randomization. This is relevant in the event of logistical issues related to scheduling of imaging (MRI, PET scans) or lumbar puncture.
- For cognitive scales, CDR and RBANS are required for eligibility. While RBANS is repeated at Baseline pre-dose, CDR is only collected once a V103 and needs to be repeated beyond 12 weeks prior to randomization.
- In such case, the corresponding repeat CDR will be collected in Virgil ideally 5 days before Randomization to allow for centralized review (if applicable). On the same day, the cognitive scales scheduled for Baseline should be administered (including RBANS Form A to verify the DMI score for inclusion). This approach leads to a split of assessments from Baseline on 2 different calendar days. Before randomization, the Diagnostic Verification Form (DVF) must be updated with the corresponding CDR and RBANS Delayed Memory Index (DMI) scores to verify eligibility. Also see [Section 6.3.4](#) for APCC requirements during Screening.

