1.1 Study design

1.1.1 Study Design Summary

The study uses a randomized, double-blind, placebo-controlled, parallel group design with variable treatment duration in cognitively unimpaired participants aged 60 to 75 years, with at least one APOE4 allele (Homozygotes (HMs) or Heterozygotes (HTs)) and if HTs, with evidence of elevated brain amyloid. Overall approximately 2000 participants were planned to be randomized into the study, with a sample size of 800 for the selected dose of CNP520 and placebo, respectively, thereby achieving a 1:1 ratio for the selected CNP520 dose vs placebo. Due to early termination of the study the original planned number of participants will not get enrolled into the study.

The various epochs in the study are specified as follows (see below [Figure 1-1](#)):

Screening Epoch

Treatment Epoch

Follow-up Epoch

Right after signing the Informed Consent (ICF#B), the screening epoch starts. The screening epoch consists of two parts: Screening I and Screening II. In Screening part I, less invasive assessments are performed and genotype is disclosed. Participant may take a few days to reflect on this information before continuing to Screening part II. Screening II includes safety assessments, various cognitive and neuropsychological scales, brain MRI scan, and mandatory amyloid PET scan or a lumbar puncture to verify eligibility of HTs based on brain amyloid status. Amyloid status will subsequently be disclosed. Although HMs are eligible regardless of their brain amyloid status (elevated/not elevated), they will also undergo a PET scan or a lumbar puncture during screening (HMs can opt out of amyloid disclosure). Another reflection period may take place after amyloid disclosure. Altogether, the screening period from signature of ICF#B (part I and part II, including reflection periods when required) is expected to last about 12 weeks.

[figure not shown]
The Treatment Epoch follows a randomized, double-blind, placebo-controlled, parallel group design in which participants receive the investigational treatments or placebo. Participants will be initially randomized to one of the treatment arms in the ratio 2:1:2 (CNP520 50 mg: 15 mg: placebo). The initial regimen is a once daily dose of 50 mg, 15 mg, or placebo throughout

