2.8.4.3 Prospective Suicidality Assessment

The Columbia-Suicide Severity Rating Scale (C-SSRS) is a questionnaire that prospectively assesses Suicidal Ideation and Suicidal Behavior. The electronic version, the eC-SSRS will be administered as described in the visit schedule of the study protocols and may also include unscheduled visits. At the first time of administration of the eC-SSRS, a retrospective assessment of suicidal behavior and ideation will be collected across lifetime. This data will be used to check inclusion/exclusion criteria. At all other scheduled assessments of suicidal behavior and ideation, any occurrence since the last visit will be collected.

The data will be reported by analysis period. The following three periods have been identified to cover lifetime history, the time between collection of lifetime history and start of study drug intake, and the time on study drug.

Tables

The number and percentage of participants pertaining to each of the categories of suicidal ideation and behaviors will be presented by analysis period and treatment.

The analysis periods will be defined as follows

1. Lifetime history: Lifetime assessment occurs only once (Screening 1 visit (Visit 101)).
2. Post disclosure pre-treatment period: assessments after the Screening 1 visit up to and including the baseline visit (Visit 103, Visit 107 and Visit 201 and unscheduled visit falling into this time period)
3. Post baseline: all visits after baseline visit (including unscheduled).

The summaries will show numbers and percentages of participants who have an answer “yes” to a suicidal behavior or ideation category at any time within the corresponding analysis period.

Listings

For participants with any assessment that meets the criteria to trigger the recording of an SAE as specified in the study protocols, a full listing will be presented. The criteria for SAE reporting are as follows:

If, at any time, the score is “Yes” on item 4 or item 5 of the Suicidal Ideation section of the C-SSRS or “Yes”. All such cases regardless of whether there was an SAE reported or not will be listed.

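### SAP 2.3.2 limits unscheduled eC-SSRS assessments to a 12-week screening period, although screening may run longer and SAP 2.8.4.3 defines the same period without that limit

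*SAP*

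**What the plan says.** Two SAP sections define an eC-SSRS period with the same name, covering the time after Visit 101 and before treatment.

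- **SAP 2.3.2 (impact of disclosure).** The period takes "Assessments after the Screening 1 visit (Visit 103, Visit 107) up to and including the baseline visit" (Visit 201), and adds any "unscheduled visit falling into 12-week Screening period". On the analysis set it states that "eC-SSRS is collected in all screened participants and will, hence, be reported based on the Screened set".
- **SAP 2.8.4.3 (prospective suicidality assessment).** The period takes "Visit 103, Visit 107 and Visit 201 and unscheduled visit falling into this time period". No number of weeks is given. Section 2.8 reports safety data on the SAF, which SAP 2.2 defines as participants who received study medication.

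On the length of screening, SAP 1.1.1 says only that it "is expected to last about 12 weeks", counted from signature of ICF#B. Protocol 3.1 adds: "The screening period can be extended on a case-by-case basis to accommodate scheduling". Protocol 6.1.6.1 sets conditions for going past 12 weeks, states no maximum, and gives amyloid PET and lumbar puncture results no expiry.

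**The concern.** One named period has two definitions, and the narrower one conflicts with the protocol's allowance for extended screening. The narrower definition also sits in the only planned eC-SSRS table that includes screen failures.

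That group matters for a disclosure analysis. Heterozygotes without elevated amyloid are ineligible (Protocol 4.1, inclusion 7b), and Protocol 3.2 assumes that 50% of heterozygotes aged 60 to 75 are in that position. They can receive an amyloid result and leave without ever entering the SAF. If a positive suicidality response from such a person is cut by a date rule, no other eC-SSRS table picks it up. Suicidality is among the outcomes this analysis exists to report, so losing even one assessment through loose wording is undesirable.

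**Working it through.** There is no planned figure to reproduce. The check traces each route by which a suicidality finding could reach a summary table.

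**Example (assumed dates).** Amyloid PET in week 13, disclosure in week 14, eC-SSRS positive in week 15, participant screen-fails and is never dosed. Such dates are possible because screening may be extended and the amyloid test has no expiry (Protocol 6.1.6.1).

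| Route | Rule | Result |
|---|---|---|
| Positive at scheduled Visit 107 | SAP 2.3.2 names Visit 107 without a week limit; Protocol Table 6-1, footnote 10, ties it to 2 to 7 days after amyloid disclosure | In the 2.3.2 table, at any week |
| Positive at an unscheduled visit, 2.3.2 table | Unscheduled visits limited to 12 weeks; 15 > 12 | Out, if read literally |
| Same assessment, 2.8.4.3 table | No week limit, but SAF only | Out, never dosed |
| Same finding recorded as a disclosure-related AE or SAE | SAP 2.3.2 summarises these without a week limit and includes suicidality among the possible terms | In the AE/SAE summary |

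So an unscheduled, late assessment in an undosed participant is in no eC-SSRS table. It is in no summary table at all unless the last route applies.

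**Same assessment, but the participant is randomised and dosed.** The 2.8.4.3 table counts it and the 2.3.2 table does not, although both claim to describe the same period.

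**When the unscheduled visit carries most weight.** The follow-up after amyloid disclosure may be a telephone call (Protocol 6.1). Footnote 10 then moves the eC-SSRS to the next scheduled visit, for continuing participants. A screen failure may have no such visit. For participants who meet a threshold by telephone, SAP 2.3.2 says that "an unscheduled visit to the site is warranted to collect appropriate safety measures". For these people the unscheduled assessment may be the only eC-SSRS after amyloid disclosure.

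**Start of the 12 weeks.** SAP 2.3.2 does not say from which date the 12 weeks run, so a programmer would have to choose one.

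**The case against.** The strongest reply is that the 12-week phrase is a loose name for the screening epoch. SAP 1.1.1 describes screening in those terms, and the stated end of the period in 2.3.2 is the baseline visit. On that reading nothing is lost and the two sections agree. This is plausible. It does not remove the conflict in wording: 2.8.4.3 shows that the SAP could state the rule without a number, Protocol 6.1.6.1 treats 12 weeks as a real limit with conditions for exceeding it, and a literal programmer would code a date cut.

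The second reply is that adverse events act as a backstop. SAP 2.3.2 expects an adverse event to be recorded when a threshold is met, and Protocol 6.1 requires recording of notable events after either disclosure. This largely stands, and it narrows the gap. It is not complete. The table needs the investigator to attribute the event to disclosure. Protocol 7.7 requires an SAE for suicidal behaviour only if the event was life-threatening. For screen failures, Protocol 6.2.1 keeps non-serious events unrelated to genetic disclosure in source data only, which sits badly with 6.1 and 7.1 for events related to amyloid disclosure.

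Third, part of the detail is out of sight. SAP 2.3.2 refers to the strategy of the disclosure advisory group's separate plan, and parts of the section are redacted. That plan might settle the point; the SAP as it stands does not.

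A reader might also infer more than the documents support:

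- *Any suicidality found after a late amyloid disclosure in a screen failure goes unreported.* It does not: Visit 107 is kept at any week, and disclosure-related events are summarised and listed.
- *Extensions come mainly from imaging or lumbar puncture delays, so disclosure tends to fall after week 12.* Protocol 6.1.6.1 says "This is relevant in the event of logistical issues related to scheduling of imaging (MRI, PET scans) or lumbar puncture", which explains when its validity rules apply, not what causes most extensions. Because amyloid results do not expire, screening can also be extended after an early disclosure.
- *The excluded visits are those most likely to be positive.* The threshold-driven visit applies where follow-up was by telephone. Under Protocol 7.7 the eC-SSRS is given at unscheduled visits generally.

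**Conclusion.** The inconsistency is real and should be corrected. Its consequence is confined to unscheduled assessments after week 12. In a never-dosed participant, such an assessment is missing from every eC-SSRS table, and from every summary table unless a disclosure-related AE or SAE was recorded. In dosed participants, the two tables can differ for the same period. Scheduled assessments at Visits 103, 107 and 201 are unaffected.

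This rests on a literal reading of the 12-week phrase and on the visible text of SAP 2.3.2. How many participants are affected, if any, cannot be derived from the documents. No inferential result is involved, since the disclosure analysis is descriptive.

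**What to change.** In SAP 2.3.2, delete the 12-week restriction and apply the 2.8.4.3 rule on the Screened set: include all unscheduled eC-SSRS assessments after Visit 101 up to and including Visit 201 or, for screen failures, up to the last eC-SSRS collected in the screening epoch, including post-disclosure follow-up, whatever the length of screening.

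The end point for screen failures should not be the date of screen failure. A heterozygote can fail on the central amyloid result before disclosure takes place, so a visit prompted by disclosure could fall after that date.

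The cost is one line of SAP wording and one date condition in a program, with a rerun of the table if a cut was coded. The SAP's revision history shows addenda after database lock, so a route exists. If the phrase was only a label, the change alters no result.
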